All subjects enrolled in the study will have thyroid function tests (TFT) which include serum TSH, total triiodothyronine (T3), total thyroxine (T4) and free T4 (fT4) assessed at baseline, at one month and two months following administration of ISOVUE. If TSH values are abnormal at either the one month or two month time points, further follow-up will be required at 6 and 12 months after the administration of ISOVUE to monitor subject's response and treatment (if any). Follow-up at 6 and 12 month post-dose time points will be performed using a pre-defined questionnaire.

The study will be conducted at approximately 10-20 sites in the United States.

Discussion of Study Design

The proposed study is designed as an intra-subject comparison of TSH, T3, and T4 values before and after administration of ISOVUE and will enroll pediatric subjects 0 to 3 years of age, who require a radiologic procedure with intravascular administration of ISOVUE as part of their standard of care.

The primary endpoint of this study is to evaluate the proportion of subjects exhibiting abnormal values of TSH following intravascular administration of ISOVUE. Thyroid function test data will be collected prospectively. Serum thyroid function testing at baseline, one month and two month post-dose time points will be performed at a local laboratory.

Abnormal TSH findings for subjects enrolled in the study will be compared to a reference population. As recommended by the FDA, the reference population for the study is represented by 3,214 infants who received potassium iodide prophylaxis on the second day of life at the time of the Chernobyl nuclear accident; 12 of the 3,214 infants ($p=0.003734$, 95% CI 0.002025, 0.006339) showed a transient increase of serum TSH levels and a decrease of fT4 levels after administration of potassium iodide.¹

As per FDA recommendation, sample size estimation for the current study has utilized the threshold incidence rate ($p=0.003734$) as the clinically meaningful value to rule out a safety concern about the proportion of children with abnormal TSH after exposure to ISOVUE.

Following FDA recommendations to be complied with:

- abnormal TSH in the study is defined as any TSH value above the normal age/gender-specific reference range provided by the respective local laboratories.
- hypothyroidism is defined as a TSH > 10 mIU/L (independent of fT4) or as a TSH above the normal age-specific reference range and an fT4 below the lower limit of the normal range.

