
Risk-Benefit Considerations

This study will enroll subjects who require a radiologic procedure with intravascular administration of ISOVUE as part of their standard of care; therefore, inclusion in the present clinical trial will not add any risk to the subject. Three blood draws of approximately 2.0 ml each will be performed in all subjects as part of the study, to assess serum TFTs before and after administration of ISOVUE.

Although subjects enrolled in the study will not directly benefit from this clinical trial, study results may be beneficial for pediatric subjects 0 to 3 years of age who will be exposed to iodinated contrast agents.

Study Duration

All subjects enrolled in the study will undergo the radiologic examination with administration of ISOVUE, as part of their standard of care; TFTs will be assessed at baseline, one month and two months post-dose.

If TSH values are abnormal at either the one month or two month time points, follow-up will be required at 6 and 12 months after the administration of ISOVUE to monitor subject's response and treatment (if any). Follow-up at the 6 and 12 month post-dose time points will be performed using a pre-defined questionnaire. Each follow-up will take no longer than 20 minutes.

Study Population

The study will be conducted in pediatric subjects 0 to 3 years of age, who are scheduled to undergo a radiologic procedure with intravascular administration of ISOVUE as part of their routine standard of care.

It is planned to enroll approximately 1,560 subjects in order to obtain 1,482 evaluable subjects.

Inclusion Criteria

Enroll a subject in this study if the subject meets the following inclusion criteria:

1. Is male or female from 0 to 3 years of age;
2. Is scheduled to undergo a radiologic examination that requires intravascular administration of ISOVUE as part of his/her standard of care;
3. Has normal baseline thyroid function tests (TSH, total T3, total T4, and fT4) performed at a local laboratory with blood sample obtained within one week prior to ISOVUE administration;
4. Written informed consent is obtained from the subject's parent(s) or legally acceptable representative(s) (according to local regulations) who are willing to comply with the protocol requirements.

Exclusion Criteria

Exclude a subject from this study if the subject does not fulfill the inclusion criteria, or if any of the following conditions are observed:

1. Has any known allergy to one or more of the ingredients of ISOVUE;

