Record all medications (prescription and over-the-counter) taken within 24 hours prior to investigational product administration in the Concomitant Medication section of the Case Report Form. Additionally, record newly prescribed pharmacological treatments up to 1 week after administration of ISOVUE.

Safety Assessments

Monitor for any untoward medical occurrences that occur in the subject during the timeframe associated with the ISOVUE administration.

Laboratory Evaluations

A local laboratory will perform evaluation for the analytes listed in Table A.

A screening/baseline assessment of TFTs specified in Table A will be collected within 7 days prior to the administration of ISOVUE. Results must be obtained prior to enrollment into the study. Only subjects with normal TFT values will be enrolled into the study.

Blood samples for assessment of TFTs specified in Table A below will be collected at one month and two months post-dose.

Table A: Laboratory Analytes

Thyroid function test
TSH (Thyroid Stimulating Hormone)
fT4 (free Thyroxine)
Total T3 (total Triiodothyronine)
Total T4 (total Thyroxine)

Follow-up

If TSH is abnormal at either the one month or two month time points, the subject will undergo follow-up at 6 and 12 months after the administration of ISOVUE using a pre-defined questionnaire. Clinical data to be collected at 6 and 12 month follow-up will include, among the others:

- development of new symptoms which were considered to be related to the abnormal TFT values by the subject's physician;
- need for treatment related to the abnormal TFT values observed after the administration of ISOVUE; in case of treatment, the type of treatment, dosage, dose adjustments, start date and current status of treatment (i.e. ongoing, completed, stop date, etc.) will be collected and reported in the CRF;
- results of any additional TFT assessment performed in the interval time since the previous visit;
- results of thyroid ultrasound examinations, if any performed in the interval time since the previous visit;
- exposure to any iodinated contrast agent in the interval time since the previous visit;
- exposure to any topical iodinated product in the interval time since the previous visit.

A more detailed description of clinical data to be collected during follow-up will be provided in the questionnaire which will be a part of the CRF.

Imaging Procedures

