The primary endpoint of this study is to evaluate the proportion of subjects, 0 to 3 years of age, with abnormal TSH values at either one month or two months after administration of ISOVUE. Following FDA recommendations, abnormal TSH in the study is defined as any TSH value above the normal age/gender-specific reference range provided by the respective local laboratories.

Abnormal TSH findings for subjects enrolled in the study will be compared to a reference population. As recommended by the FDA, the reference population for the study is represented by 3,214 infants who received potassium iodide prophylaxis on the second day of life at the time of the Chernobyl nuclear accident; 12 of the 3,214 infants ($p=0.003734$, 95% CI 0.002025, 0.006339) showed a transient increase of serum TSH levels and a decrease of fT4 levels after administration of potassium iodide.¹

The study hypothesis will be:

$$H_0: p \geq 0.003734$$

$$H_A: p < 0.003734$$

The proportion of subjects with abnormal TSH at either one month or two months after administration of ISOVUE and its 95% confidence interval will be estimated. Confidence interval will be calculated based on the approximate normal distribution:

$$95\% \text{ CI} = p \pm 1.96 * (p * (1-p) / n)^{1/2}$$

The number of subjects with shift in serum TSH (with respect to normal reference range) after exposure to ISOVUE will be cross tabulated and summarized separately. Each subject will serve as his/her own control, with the pre-dose values representing their baseline or control values.

Secondary Endpoint - Analysis for Hypothyroidism

The secondary endpoint is to evaluate the proportion of subjects, 0 to 3 years of age, with hypothyroidism regardless of the need for thyroid hormone therapy at either one month or two months after administration of ISOVUE.

Hypothyroidism is defined as a TSH $> 10 \text{ mIU/L}$ (independent of fT4) or as a TSH above the normal age/gender-specific reference range and a fT4 below the lower limit of the normal range.

The proportion of subjects with hypothyroidism at either one month or two months after administration of ISOVUE will be estimated and the 95% confidence interval will be presented.

For those subjects with hypothyroidism, follow-up data will be summarized by monitoring time points (6 months and 12 months).

Secondary Endpoint - Analysis for Thyroid Hormone Replacement Therapy

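### The fixed TSH > 10 mIU/L limb of the hypothyroidism definition is not tied to the local range that governs entry, the primary endpoint and the follow-up trigger, so some hypothyroidism cases could lack the 6- and 12-month data the protocol plans to summarise

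*Protocol*

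**What the plan says.** Four rules in the protocol bear on this point.

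- **Hypothyroidism (first secondary endpoint).** The definition appears in Discussion of Study Design and in Secondary Endpoint - Analysis for Hypothyroidism. It has two limbs. The first is a fixed cut-off: "hypothyroidism is defined as a TSH > 10 mIU/L (independent of fT4". The second depends on the range: "or as a TSH above the normal age/gender-specific reference range and a fT4 below the lower limit of the normal range".
- **Abnormal TSH (primary endpoint).** Only the range counts: "any TSH value above the normal age/gender-specific reference range provided by the respective local laboratories".
- **Entry.** Inclusion criterion 3 asks that the child "Has normal baseline thyroid function tests (TSH, total T3, total T4, and fT4) performed at a local laboratory", and Laboratory Evaluations adds: "Only subjects with normal TFT values will be enrolled into the study". Neither sets a fixed TSH ceiling. Inclusion criterion 1 sets no minimum age.
- **Late follow-up.** The Follow-up section makes abnormal TSH the only trigger: "If TSH is abnormal at either the one month or two month time points, the subject will undergo follow-up at 6 and 12 months". Discussion of Study Design and Study Duration say the same. The hypothyroidism analysis nevertheless plans: "For those subjects with hypothyroidism, follow-up data will be summarized by monitoring time points (6 months and 12 months".

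**The concern.** One rule is an absolute number and the others move with the laboratory and the child's age. They agree only while every applicable upper limit is 10 mIU/L or lower. The protocol does not require this, and it does not say which rule governs if a limit is higher.

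Two things are at stake. First, the planned 6- and 12-month summary of hypothyroid children would be incomplete by design, because some of those children would never be sent the questionnaire. Second, the protocol describes an intra-subject design in which each child is his or her own control. A child who met the TSH > 10 limb before ISOVUE could still be counted after it, even if TSH had fallen. The hypothyroidism proportion could then not be read cleanly as a change from before to after exposure.

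**Working it through.** **The plan's own figures.** The sample size follows from the rule of three: 3 / 0.002025 = 1,481.5, rounded up to 1,482. Allowing for 5% dropout, 1,482 / 0.95 = 1,560. Both figures reproduce, and neither depends on the hypothyroidism definition.

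**Notation.** T is the TSH at a visit and U is the local upper limit that applies to the child at that visit. The protocol gives no value of U, so the values below are illustrations.

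**Step 1: where the definitions part.**

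- Abnormal TSH: T > U.
- Hypothyroidism: T > 10, or (T > U and fT4 low).
- Hypothyroid but not abnormal: T must be at or below U, which rules out the second limb. What is left is 10 < T ≤ U.

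This interval is empty when U ≤ 10. The range-based limb never causes a conflict; only the fixed limb can.

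**Step 2: trial values of U,** checked against TSH of 4, 6, 9, 10.5, 11, 13, 18 and 25, with fT4 low or not.

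| U (mIU/L) | TSH values that are hypothyroid but not abnormal |
|---|---|
| 5, 8, 10 | none |
| 12 | 10.5, 11 |
| 15 | 10.5, 11, 13 |
| 20 | 10.5, 11, 13, 18 |

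**Step 3: follow-up.** The relevant U is the one at month 1 or month 2. A child with 10 < T ≤ U at one visit, and no value above range at the other, is a hypothyroidism case and a primary non-case. The Follow-up section then sends no questionnaire, although the analysis section plans to summarise its data.

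**Step 4: baseline.** The relevant U is now the one at entry. Inclusion criterion 3 says only that tests are normal at a local laboratory. Reading that as the local range is fair, though not spelled out. If U exceeds 10 at entry, a baseline T in (10, U] is normal, so the child is enrolled while already meeting the first limb.

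**Step 5: the two effects are separate.** Take a baseline TSH of 11.5 with U = 12, and a month-1 TSH of 10.5.

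- If U is still 12 at both post-dose visits and no value exceeds it, the child is a hypothyroidism case, a primary non-case and without a questionnaire. TSH fell from 11.5 to 10.5.
- If U has dropped to 10 by month 1, the same 10.5 is above range. The child is then a case on both endpoints and is followed. Only the baseline problem remains.

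**Step 6: scale.** With 1,482 evaluable children, each affected child moves the hypothyroidism proportion by 1 / 1,482 = 0.067 percentage points. The number affected cannot be derived from the document.

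**The case against.** The strongest reply is that the conflict is conditional and its condition is not shown. No section gives a local range, and none says that any upper limit exceeds 10. For follow-up, moreover, what counts is the limit one or two months after dosing. Even a child dosed on the day of birth is then about one month old or older, so the newborn range bears only on entry. Both points stand.

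A second reply is that the definition is deliberate. The protocol presents both definitions as regulatory recommendations to be followed, and nothing says that hypothyroidism must be a subset of abnormal TSH or must be new. This also stands, and it is a reason to leave the stated endpoint as it is. It does not reconcile the questionnaire trigger with the planned summary.

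A third reply is that all data will be listed, that pre-dose values serve as the control, and that tabulation detail can wait for the SAP. This holds for how cases are split by baseline status. It does not hold for the questionnaire, because an analysis plan cannot supply data that the protocol never collects.

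A reader might infer three stronger things that the documents do not support.

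- *That the hypothyroidism rate will be materially inflated.* Suppose 5% to 20% of children have U > 10 and 1% to 5% of those fall in the gap. The count then runs from 1,482 × 0.05 × 0.01 = 0.7 to 1,482 × 0.20 × 0.05 = 14.8. That twenty-fold spread comes entirely from assumed inputs, and the true figure may be zero.
- *That such counts should be set against the threshold of 0.003734 × 1,482 = 5.5 cases.* That threshold belongs to the primary hypothesis on abnormal TSH. Hypothyroidism is only estimated, with a 95% confidence interval and no test.
- *That these children are never followed.* Only the 6- and 12-month study questionnaire is missing. A child flagged at month 1 is still due the month-2 tests, and routine care is not excluded.

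**Conclusion.** The point holds as a conditional inconsistency. If a local upper limit exceeds 10 mIU/L at month 1 or 2, the protocol creates hypothyroidism cases for whom it plans a 6- and 12-month summary but triggers no data collection. If a limit exceeds 10 at baseline, the hypothyroidism proportion can also include children who met the TSH > 10 limb before exposure, which sits badly with the own-control design.

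The first part rests on the protocol's wording alone. The second also rests on reading normal baseline tests as within the local range. The frequency is unknown from the documents, and is zero if no local limit exceeds 10. The effect is confined to one secondary endpoint and to the completeness of its follow-up; the primary hypothesis and the sample size are untouched. The passages should be reconciled. Which TSH cut-off is clinically right is not judged here.

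**What to change.** 1. In Follow-up, and in the matching text of Discussion of Study Design and Study Duration, trigger the existing 6- and 12-month questionnaire for any child who meets either the abnormal-TSH or the hypothyroidism definition at month 1 or 2. The planned summary then covers every hypothyroidism case.
2. In Secondary Endpoint - Analysis for Hypothyroidism, keep the stated proportion unchanged. Beside it, add a supplementary count that excludes children who already met the definition at baseline, and show TSH > 10 within the local range separately.

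The cost is a wording change, one extra table row, and up to two questionnaires of at most 20 minutes for each additional child. It needs no further blood draws or subjects. Because the original proportion is still reported, the endpoint remains as recommended.

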2. Has been diagnosed with congenital hypothyroidism;
3. Has undergone radiation treatments to the head or neck;
4. Is currently on thyroid replacement therapy;
5. Is on therapy with dopamine or any treatment which may affect the thyroid function testing results;
6. Has been exposed to any topical iodinated product within 30 days prior to enrollment in the present study;
7. Has been exposed to an iodinated contrast agent within 1 year prior to enrollment in the present study, including any administration of iodinated contrast agents during placement of a central line;
8. Has any medical condition or other circumstances which would significantly decrease the chances of obtaining reliable data, achieving study objectives, or completing the study and/or post-dose follow-up examinations.

Discontinuation Criteria

Clearly document the reason for the subject's discontinuation on the Case Report Form. Discontinued subjects are not replaced. Discontinue a subject from the study if the subject:

- Withdraws consent;
- No longer meets the Inclusion Criteria;
- Is lost to Follow Up

Investigational Products

The investigational product is ISOVUE® (Iopamidol Injection).

ISOVUE will not be provided to the participating sites since the study will enroll subjects undergoing a radiologic examination with intravascular administration of the contrast agent as part of their standard of care.

Methodology

Subject Evaluations

Demographic Information

Collect the following demographic information for subject's enrolled in the study:

- Date of Birth
- Gender
- Race
- Height (cm)
- Weight (kg)

Medical History

Obtain a complete medical history of subjects enrolled in the study, within 24 hours prior to the administration of ISOVUE. Report any clinical condition that might predispose to thyroid function abnormalities such as

- pre-term birth
- low or very low birth weight
- mother's exposure to iodinated contrast agents, iodine containing medications (e.g., Amiodarone, Potassium iodide), or topical iodinated product during pregnancy
- diagnosis of Down's Syndrome or other chromosomal abnormalities, congenital diseases, or Type I diabetes
- results of neonatal screening of thyroid function testing
- previous exposure to iodinated contrast agent (greater than 12 months prior enrollment in the present study).

Concomitant Medications

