The proportion of subjects initiated on thyroid hormone replacement therapy will be estimated with 95% confidence interval.

Analysis for Other Safety Issues

Serious adverse events and non-serious adverse drug reactions will be summarized and listed.

Sample Size

The threshold incidence rate ($p=0.003734$) obtained from the Nauman and Wolff publication¹ will be used as the clinically meaningful value to rule out a safety concern about the proportion of children with abnormal TSH after exposure to ISOVUE. Using confidence interval method for the probability of observing a rare event, when no case is observed out of n , the upper 95% confidence limit of the incidence rate can be estimated by $3/n$. If no cases were observed in the sample size of 1,482, there is 95% confident to rule out an incidence rate of 0.002025 or higher. Considering a 5% drop out rate, 1,560 subjects will be enrolled in the study.

Interim Analyses

No interim analysis is planned.

References

¹ Nauman J, Wolff J. Iodide prophylaxis in Poland after the Chernobyl reactor accident: benefits and risks. Am J Med. 1993 May;94(5):524-32.

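### A high TSH found and treated before month 1 can go uncounted, while the safety claim is worded as abnormal TSH after exposure

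*Protocol*

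**What the plan says.** - **Threshold.** Sample Size: "The threshold incidence rate ($p=0.003734$) obtained from the" cited publication is the "clinically meaningful value to rule out a safety concern about the proportion of children with abnormal TSH after exposure to ISOVUE". The alternative hypothesis is "H_A: p < 0.003734".
- **Reference event.** Primary Endpoint: the threshold is 12 of "3,214 infants who received potassium iodide prophylaxis on the second day of life", who "showed a transient increase of serum TSH levels and a decrease of fT4 levels after administration of potassium iodide". When those infants were sampled, and how long the rises lasted, is not stated.
- **Sampling.** Laboratory Evaluations: "Blood samples for assessment of TFTs specified in Table A below will be collected at one month and two months post-dose". No earlier post-dose sample is planned.
- **Endpoints.** Abnormal TSH and hypothyroidism are both defined at month 1 or month 2. Hypothyroidism is to be counted whether or not treatment is needed. The proportion started on thyroid hormone replacement is a further secondary endpoint, with no time point.
- **Data collection.** Concomitant Medications: newly prescribed drugs are recorded for one week after dosing. Follow-up: only a child with abnormal TSH at month 1 or 2 gets the 6- and 12-month questionnaire, which covers thyroid treatment and "results of any additional TFT assessment performed in the interval time since the previous visit".

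**The concern.** The claim is wider than the data behind it. The Sample Size wording covers abnormal TSH after exposure without a time limit, and the benchmark event is called transient. The endpoint sees only what is present at two scheduled samples, the first a month after dosing.

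The more practical problem is data capture. If a clinician finds a high TSH in, say, week 2 and treats it successfully, nothing in the stated collection rules brings that child into any endpoint. Such a child may be among the more severe cases. The replacement-therapy endpoint exists to count such children, but it has no matching data source when TSH is in range at both months. An analysis plan cannot repair this later, because it cannot use test results and treatment starts that were never collected.

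**Working it through.** **1. The plan's own figures reproduce.** 12/3,214 = 0.003734. Rule of three: 3/0.002025 = 1,481.5, so 1,482 evaluable; 3/1,482 = 0.002024. Dropout: 1,482/0.95 = 1,560. The sample size arithmetic is not in question.

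**2. One child traced through the protocol.** Normal at baseline; high TSH on a clinical test in week 2; thyroid hormone started then; TSH in range at months 1 and 2.

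| Section | Rule | Result for this child |
|---|---|---|
| Analysis Population | Dosed, TSH at month 1 or 2 | In the denominator |
| Primary endpoint | TSH above range at month 1 or 2 | Non-case |
| Hypothyroidism | Criteria met at month 1 or 2 | Non-case, because treatment worked |
| Concomitant Medications | New drugs to one week | Start not recorded |
| Follow-up | Abnormal TSH at month 1 or 2 | No questionnaire |
| Replacement therapy | Initiated on therapy | Counts by definition; no stated data source |

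A child treated within week 1 would have the drug recorded, but would still be a non-case for the first two endpoints. A child whose rise resolved untreated before month 1 is also a non-case for both.

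**3. Illustration of size.** Assumptions:
- The true any-time rate equals 0.003734.
- A share s of rises is still visible at month 1 or 2. The documents give no value for s, so a range is shown.
- The trial passes if the upper limit of the protocol's interval is below 0.003734.

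With n = 1,482 the upper limit for x cases is x/n + 1.96 × √[(x/n)(1 − x/n)/n]:
- x = 2: 0.00135 + 0.00187 = 0.00322, pass.
- x = 3: 0.00202 + 0.00229 = 0.00431, fail.

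So up to 2 cases pass. Visible cases are X ~ Binomial(1,482, 0.003734 × s). The last column takes the protocol's zero-case scenario: the any-time rate then excluded is 3/(1,482 × s).

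| s | Expected visible cases | P(X ≤ 2) | P(X = 0) | Any-time rate excluded by zero cases |
|---|---|---|---|---|
| 1 | 5.53 | 0.0859 | 0.0039 | 0.00202 |
| 0.75 | 4.15 | 0.2165 | 0.0157 | 0.00270 |
| 0.5 | 2.77 | 0.4772 | 0.0627 | 0.00405 |
| 0.25 | 1.38 | 0.8376 | 0.2506 | 0.00810 |

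The last column reaches 0.003734 at s = 3/(1,482 × 0.003734) = 0.54. Below that share, even zero observed cases would not exclude the threshold as an any-time rate. The 0.0859 at s = 1 comes from the normal-approximation interval and is a separate matter.

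**4. The opposing force.** The reference event required a TSH rise and an fT4 decrease. The trial counts TSH above range alone, on either of two occasions. Suppose this adds a fraction e of unrelated exceedances (also an assumption), so that the observed rate is 1 − (1 − 0.003734 × s)(1 − e). At s = 0.5, P(X ≤ 2) falls from 0.4772 to 0.2038 for e = 0.1%, to 0.0438 for e = 0.25%, and to 0.0024 for e = 0.5%.

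**The case against.** The objective, the primary endpoint and the estimated proportion all state the month 1 or 2 window openly. The unrestricted phrase stands only in the sample size rationale and is not a stated conclusion. This is fair: the endpoint is not mis-scored, and the rewording needed is small.

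Three stronger readings are tempting, and the documents do not support them.

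- *That the trial as a whole is biased toward ruling out a concern.* Missed early rises can only lower the count, but the TSH-only definition can only raise it relative to the reference event. Step 4 shows that a small assumed excess can outweigh the first effect. The timing of the reference measurements is also not given; if those infants were sampled at similar times, the mismatch in window would shrink or disappear.
- *That every endpoint depends on scheduled samples.* The replacement-therapy endpoint does not. Its weakness is in collection, not definition.
- *That the protocol itself treats iodine effects as over by month 1*, because one exclusion reads "Has been exposed to any topical iodinated product within 30 days prior to enrollment in the present study". That is a pre-enrolment rule for topical products and says nothing about how long an effect lasts. The next criterion, for iodinated contrast, uses 1 year.

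Two further points count against the concern. The use of unscheduled laboratory values is often left to an analysis plan; that covers how they are analysed, not whether they are collected. And an early treated case might surface as an adverse drug reaction, or through CRF detail not shown here. But the safety monitoring period has no stated end, and no rule carries such a report into an endpoint.

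**Conclusion.** The concern holds in limited form. By the stated rules, a child whose high TSH was found and treated to normal between week 1 and month 1 is a non-case for abnormal TSH and hypothyroidism, gets no 6- or 12-month follow-up, and can be missed by the replacement-therapy endpoint. The Sample Size wording also claims more than a month 1 or 2 proportion can show.

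How many children this affects cannot be taken from the protocol. The rise in the pass probability from 0.09 to 0.48 at s = 0.5 is an illustration. It rests on an assumed missed share, on reading 0.003734 as an any-time rate, and on no unrelated exceedances. The net direction of bias in the comparison is not established. The sample size is unaffected. The change is worth making because it is cheap and the lost information cannot be recovered afterwards.

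**What to change.** 1. At the month-1 and month-2 visits, ask all subjects for the results of any thyroid function test since the previous visit and for any thyroid hormone started, with dates. Use this as the data source for the replacement-therapy endpoint.
2. Add a supportive analysis that counts as a case any post-dose TSH above range, scheduled or not, or any thyroid hormone start, up to the month-2 visit. Collect the existing 6- and 12-month questionnaire for those children as well. The primary endpoint stays as it is.
3. In Sample Size, restrict the claim to abnormal TSH present at one or two months after ISOVUE, and state that earlier transient rises are not assessed.

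The cost is one existing questionnaire item, extended to thyroid hormone starts, at two existing visits; the questionnaire for any further children identified; one supportive analysis; and a narrower sentence. No blood samples are added. The downside is that unscheduled tests are done selectively, so the supportive count is incomplete. Rises that no one tested for before month 1 remain unmeasured, and only the third change deals with them.

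### The sample-size claim rests on a one-sided 95% limit and the primary interval is two-sided 95%; no stated level links them, and the Wald formula hides the difference

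*Protocol*

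**What the plan says.** The Sample Size section of the protocol uses the rule of three: with no events in n, "the upper 95% confidence limit of the incidence rate can be estimated by" 3/n. It then claims: "If no cases were observed in the sample size of 1,482, there is 95% confident to rule out an incidence rate of 0.002025 or higher". Enrolment follows from that number: "Considering a 5% drop out rate, 1,560 subjects will be enrolled in the study". The figure 0.002025 is the lower end of the interval that the protocol gives for the reference rate of 12 in 3,214 ("95% CI 0.002025, 0.006339").

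The section Primary Endpoint - Analysis for Abnormal TSH sets a one-sided hypothesis. The null is a rate of 0.003734 or more and the alternative is a lower rate. For the analysis, the proportion is to be reported "and its 95% confidence interval will be estimated". The method is fixed: "Confidence interval will be calculated based on the approximate normal distribution", with multiplier 1.96. The protocol gives no significance level and does not say which limit, compared with which value, rejects the null.

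**The concern.** Both sections say 95% but mean different tails. The rule of three comes from -ln(0.05) = 2.996, so it leaves 5% above the limit. A 1.96 interval nominally leaves 2.5% above its upper end. The property that justifies 1,482 children is therefore stated at a weaker level than the only interval specified for the primary endpoint.

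Two things are at stake. The first is whether the ruling-out claim can be repeated in the report beside the primary interval. The second is whether a small non-zero count could be read as success or failure according to a level chosen after the data are seen.

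**Working it through.** **Inputs.** From the Sample Size section: n = 1,482 evaluable, zero cases, target rate 0.002025, 5% dropout. From the primary endpoint section: threshold p0 = 0.003734 and the interval p ± 1.96·√(p(1−p)/n).

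**Reproducing the plan.** 3/0.002025 = 1,481.5, rounded up to 1,482. Back again, 3/1,482 = 0.002024. The exact one-sided 95% limit is 1 − 0.05^(1/1482) = 0.002019. Enrolment is 1,482/0.95 = 1,560. The stated figures are correct as one-sided 95% figures.

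**Zero cases at the level of the primary interval.** With 2.5% in the upper tail, −ln(0.025) = 3.689. The limit is 3.689/1,482 = 0.002489, or exactly 1 − 0.025^(1/1482) = 0.002486. This is above 0.002025. To exclude 0.002025 at this level, zero cases would be needed in ln(0.025)/ln(1 − 0.002025) = 1,819.8, so 1,820 evaluable children. Against the actual threshold, (1 − 0.003734)^1482 = 0.0039, so zero cases rejects the null at either level.

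**Upper limits by number of cases, n = 1,482, to be compared with 0.003734.** Exact limits are Clopper-Pearson.

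| Cases | Wald, z = 1.645 | Wald, z = 1.96 | Exact, one-sided 95% | Exact, two-sided 95% | P(X ≤ x) at p0 |
|---|---|---|---|---|---|
| 0 | 0 | 0 | 0.002019 | 0.002486 | 0.0039 |
| 1 | 0.001784 | 0.001997 | 0.003197 | 0.003754 | 0.0256 |
| 2 | 0.002918 | 0.003219 | 0.004242 | 0.004866 | 0.0859 |
| 3 | 0.003945 | 0.004313 | 0.005224 | 0.005904 | 0.1974 |

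As an example of the Wald column, one case gives p = 1/1,482 = 0.000675 and a standard error of 0.000675, so the upper limit is 0.000675 + 1.96 × 0.000675 = 0.0020.

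**Reading the table.** The two Wald columns give the same decisions: zero, one and two cases fall below 0.003734 and three do not. At zero cases the Wald interval is [0, 0], which cannot yield 3/n or 3.69/n. It also lets two cases pass although the exact probability of two or fewer at p0 is 0.086. The exact columns differ in one row: one case is below the threshold one-sided and just above it two-sided. The Wilson score interval shows the same split: 0.00302 and 0.00381 for one case, 0.00182 and 0.00259 for zero cases.

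**How likely is one case?** The protocol gives no expected rate. If the true rate is assumed to be 0.0005, 0.001, 0.0015 or 0.002025, the probability of exactly one case in 1,482 is 0.35, 0.34, 0.24 or 0.15.

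**The case against.** The case for the protocol is substantial. An upper 95% limit is ordinary wording for a one-sided bound, it matches the one-sided hypothesis, and its arithmetic is right. Reporting a two-sided interval beside a one-sided sizing bound is common practice. The primary endpoint section says only that the interval is estimated, not that its upper end decides, and a significance level may well stand in an analysis plan that is not at hand. The value 0.002025 is not the null threshold. Under the formula actually specified, the choice of level changes no decision.

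Most of this stands. Two points do not fall to it. The protocol itself fixes two tail levels under one label, so the ambiguity is already in the text and is not merely detail deferred. And the formula that makes the level harmless does so because it fails for rare events: it gives no usable limit in the very zero-case scenario on which the study is sized.

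A reader might infer more, and the documents do not support it:

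- That one case passes or fails under the present plan according to the level. It passes at both levels with the specified formula. The reversal needs an exact or score interval, which the protocol does not name. A mid-P interval would not show it either (two-sided 95% limit about 0.0033).
- That a handful of children decides the result. With one case, the exact two-sided limit falls below the threshold from n = 1,490, eight more than planned, but this too presupposes a rule that the protocol does not contain.
- That the study is too small and needs 1,820 evaluable children. That number serves only the 0.002025 claim at the stricter level; zero cases clears 0.003734 at 1,482 either way.

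**Conclusion.** The mismatch is real but limited in effect. The claim about 0.002025 is a one-sided 95% statement. At the two-sided 95% level of the primary interval the zero-case limit is 0.00249, about 23% higher (0.002486/0.002025 = 1.23), so the claim cannot stand beside that interval unqualified. The conclusion against 0.003734 with zero cases is unaffected.

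The level begins to matter for the hypothesis once the Wald formula is replaced by an exact interval, as it should be for counts this small. Then one case in 1,482 is decided by the choice of level alone (0.00320 against 0.00375, exact P = 0.0256). This rests on exactly 1,482 evaluable children and on the upper limit being the deciding quantity. If all 1,560 were evaluable, one case would pass at both levels (exact two-sided limit 0.00357).

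**What to change.** In the primary endpoint section, state one level. Add the rule that the null is rejected when the upper limit is below 0.003734, and compute that limit by Clopper-Pearson in place of the normal approximation. Aligning the level alone would not be enough, because the Wald formula still returns [0, 0] at zero cases.

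In the Sample Size section, choose the matching wording:

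- If one-sided 5% decides, label 3/n as a one-sided 95% limit. The 0.002025 statement can then stay.
- If the two-sided 95% interval decides, restate the zero-case limit as about 0.0025 (3.69/n), note that it lies below 0.003734, and drop the claim to rule out 0.002025.

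Keep the sample size. The drafting cost is a few sentences and, under the second option, one less favourable figure. The limits also become wider, with a practical consequence at n = 1,482: two cases, which pass under the Wald formula, no longer pass. One case is still allowed at one-sided 5%, and none at the two-sided 95% level. The sponsor should choose the level knowing this, and before any outcome data are reviewed.
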